Specific Aim 1. We will recruit 15 runners; ten with unilateral and five with bilateral transtibial amputations that currently use and have at least one year of experience with distance-running RSPs. Subjects will be between 18-55 years old and have no current problems with their prosthesis or residual limb. There will be no restrictions on sex, race, or ethnicity for inclusion. Subjects will be at a K4 Medicare Functional Classification Level, which is defined as a person who has the ability or potential for prosthetic ambulation that exceeds basic ambulation skills, exhibiting high impact, stress, or energy levels. Subjects will have no known cardiovascular, pulmonary, or neurological disease or disorder. These inclusion/exclusion criteria will minimize any potential confounding variables, thereby increasing the internal validity of the proposed studies. Any person matching the inclusion criteria of the study, regardless of race or gender, will be recruited to participate.

Specific Aim 2. We will recruit 15 sprinters; ten with unilateral transtbial amputations and five with bilateral transtibial amputations that currently use and have at least one year of experience with sprint-running RSPs. Subjects will be between 18-55 years old and have no current problems with their prosthesis or residual limb. There will be no restrictions on sex, race, or ethnicity for inclusion. Subjects will be at a K4 Medicare Functional Classification Level, which is defined as a person who has the ability or potential for prosthetic ambulation that exceeds basic ambulation skills, exhibiting high impact, stress, or energy levels. Subjects will have no known cardiovascular, pulmonary, or neurological disease or disorder. These inclusion/exclusion criteria will minimize any potential confounding variables, thereby increasing the internal validity of the proposed studies. Any person matching the inclusion criteria of the study, regardless of race or gender, will be recruited to participate.

[figure not shown]

Figure 2. Overview of the experimental design. We will vary distance-running RSP (*Specific Aim 1*) and sprint-running RSP (*Specific Aim 2*) stiffness (k) and height (h) to create guidelines for prosthetic prescription.

C. Study Design and Research Methods

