The study will be a repeated-measures design. We will calculate subject and group averages for each condition from data normalized to a gait cycle. The data analyzed will include: leg stiffness, peak vertical and horizontal ground reaction forces, stance time, leg swing time, metabolic costs, top speed, peak socket pressure, and maximum socket motion. We will use repeated measures analysis of variance (ANOVA) to compare each variable across all conditions. Any significant differences will be further analyzed with either a Tukey HSD or Newman-Keuls follow-up procedure. In the case of an unequal number of subjects, we will use a Sheffe follow-up procedure. We will use p < 0.05 as a criterion for determining statistical significance. All statistical analyses will be performed with JMPIN software (JMPIN, SAS Institute, Cary, NC).

Specific Aim 1. Subjects will complete six experimental sessions at the University of Colorado Locomotion Lab; each session on a separate day and requiring approximately two hours of time. During each experimental session, subjects will run at two speeds, the speed required for their age/sex 50th percentile PFT (Physical Fitness Test) 2 mile run and a standard speed of 3 m/s on a force measuring treadmill while we measure their ground reaction forces, metabolic demand, socket pressures, and socket pistoning. Subjects will run with three different brands (Ossur,

Ottobock, and Freedom Innovations) of distance-running RSPs with three different stiffnesses at one height and three different heights at one stiffness of each brand, a total of five or more different conditions per brand at two speeds. Individual trials will be five minutes long with at least 2 minutes rest between trials.

Day DR0: Subjects will be asked to give informed written consent and then will be fit and aligned by a certified prosthetist with three different distance-running RSP brands, one from each company. We will measure each subject's height, weight, and limb segment lengths. Then, we will select an RSP stiffness category based on the subject's weight and manufacturer's recommendation. An appropriate RSP height for each subject will be chosen according to conventional practice. Our prosthetist will ensure that the prosthetic fit and alignment are adequate. Then, subjects will have time to accommodate to treadmill running with each distance-running RSP.

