Days SR4 and SR6: We will repeat the trials of Day SR2 and vary height (h) for a different sprint-running RSP brand. We will analyze the results of Days SR4 and SR6 to identify the optimal height (h_{ort}) for each subject using the respective brand of a sprint-running RSP.

Measurements and Analysis:

Ground Reaction Forces. We will measure ground reaction forces at 1000 Hz using a 3-D force-measuring treadmill (Treadmetrix, Park City, UT) for at least 10 strides (approximately 15 sec) per trial. Then, we will filter the ground reaction forces using a 4th order Butterworth low pass filter using a custom software program (Matlab, Mathworks, Natick, MA). We will then use a spring-mass model to calculate each leg's overall stiffness (Farley & Gonzalez, 1996). To understand the effects of multiple speeds and prosthetic stiffness during running, we will calculate and compare leg stiffness. Leg stiffness equals the peak ground reaction force divided by peak leg compression. Leg compression is calculated as the change in distance from the center of mass to the point of ground contact (Blickhan & Full, 1993; Cavagna, 1975; Farley & Ferris, 1998). We will calculate center of mass displacement by twice integrating center of mass acceleration, which is calculated from the ground reaction force.

Metabolic Demand. Each running trial in Specific Aim 1 will be five minutes long with at least two minutes rest between trials. We will measure rates of oxygen consumption and carbon dioxide production using indirect calorimetry (ParvoMedics TrueOne 2400, Sandy, UT). We will calculate average steady-state metabolic power (W) from minutes 3-5 of each trial using a standard equation (Brockway, 1987). In our experience, a trial length of five minutes is sufficient for subjects to reach steady-state metabolic rate.

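### Aim 1 metabolic power is specified in watts with weighing stated only on Day DR0, so body-mass change between sessions adds avoidable error to the brand contrasts and to the choice of height

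*Combined protocol and SAP*

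**What the plan says.** Under Metabolic Demand in Section IV.C (Measurements and Analysis), the outcome is defined thus: "We will calculate average steady-state metabolic power (W) from minutes 3-5 of each trial using a standard equation". No section divides it by body mass or by distance. The only normalisation named is in the opening paragraph of Section IV.C: "We will calculate subject and group averages for each condition from data normalized to a gait cycle". That is a time base and does not deal with mass.

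For Aim 1, weighing is scheduled on Day DR0: "We will measure each subject's height, weight, and limb segment lengths". There it serves to select the stiffness category. The descriptions of Days DR1 to DR6 list no further weighing. Section IV.F names weight among the data to be obtained but gives no timing.

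The six sessions are described as "each session on a separate day and requiring approximately two hours of time", with no maximum interval between them. Days DR1 and DR2 cover one brand, DR3 and DR4 a second, DR5 and DR6 a third. No method for ordering the brands is stated. Within a brand, the three stiffness conditions are run on one day. The recommended height is taken from that day, and the shorter and taller heights are run on the next session. Runners use two speeds: a common 3 m/s and "the speed required for their age/sex 50th percentile PFT (Physical Fitness Test) 2 mile run".

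On analysis: "We will use repeated measures analysis of variance (ANOVA) to compare each variable across all conditions". The criterion is p < 0.05, and the sample is 15 runners.

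**The concern.** Running power rises roughly with the mass carried, so a runner who is heavier on one test day than on another will tend to show more watts on that day whatever prosthesis is worn. Two kinds of comparison in the plan cross days:

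- **Brand.** Every brand contrast compares different days.
- **Height.** The recommended height is compared with heights measured on a later day. A mass change between those days moves the shorter and taller conditions together against the recommended one, and so pushes the choice towards or away from it. This choice is made for one subject at a time, so averaging over 15 runners does not protect it. Section IV.D promises each subject a recommendation at the end of the study.

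At stake is precision in the outcome that selects the prosthesis. A mass that was neither recorded nor derived for the test day cannot be supplied reliably afterwards.

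**Working it through.** The documents give no variance, effect size or power figure for metabolic power, so there is no stated figure to reproduce. Every mass, W/kg value and error size below is an assumption.

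**1. Which comparisons cross days** (Section IV.C, Days DR1 to DR6)

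| Comparison | Days | Exposed to mass change between days? |
|---|---|---|
| Stiffness within a brand | DR1 (likewise DR3, DR5) | No: same day, and dividing by one mass keeps the ranking |
| Recommended height against shorter or taller | DR1 against DR2 (likewise DR3/DR4, DR5/DR6) | Yes |
| Shorter against taller | DR2 (likewise DR4, DR6) | No: same day |
| Brand against brand | DR1-2, DR3-4, DR5-6 | Yes |

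**2. Size of one mass change.** Assume a 75 kg runner at 12 W/kg. A change of 1 kg is 1/75 = 1.3%, or 12 W (10 to 15 W at 10 to 15 W/kg). A change of 2 kg is 2/75 = 2.7%, or 24 W (20 to 30 W).

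**3. Added variance.** Assume other error of 2% and power proportional to mass. With between-day mass SD s (in %), total SD = sqrt(2² + s²).

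- s = 0.5: sqrt(4.25) = 2.06%; variance ratio 4.25/4 = 1.06
- s = 1: sqrt(5) = 2.24%; ratio 5/4 = 1.25
- s = 2: sqrt(8) = 2.83%; ratio 8/4 = 2.00

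**4. Effect on power for a brand contrast.** Assume a true difference of 2%, n = 15, a paired t test at two-sided 0.05, and SD of the difference = sqrt(2) × sqrt(2² + s²).

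| Mass SD | SD of difference | Power |
|---|---|---|
| 0 | 2.83% | 0.72 |
| 0.5% | 2.92% | 0.70 |
| 1% | 3.16% | 0.63 |
| 1.5% | 3.54% | 0.53 |
| 2% | 4.00% | 0.44 |

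**5. Weight given to heavier or faster runners.** Adding an arbitrary constant to each subject leaves the repeated-measures F unchanged (0.5215 before and after), so a runner's overall level of watts does not affect the condition contrasts. Suppose instead that condition effects are proportional to mass, with 15 masses evenly spaced from 50 to 100 kg (sum 1125 kg). The lightest runner's share of the group effect is 50/1125 = 4.4% and the heaviest's 100/1125 = 8.9%, against an equal share of 1/15 = 6.7%. The effective n, (Σw)²/Σw², is 14.4 of 15. In a worst case where effects scale with mass × speed, and the heaviest runner is also the fastest (2.5 to 4.0 m/s), shares run from 3.3% to 10.6% and effective n is about 13.5.

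**6. Scaling alone.** In simulated paired tests with a fixed mass per runner (50 to 100 kg, 2% error, 2% effect, n = 15), power is 0.71 in W and 0.72 in W/kg, with type I error of 0.050 and 0.051. Dividing by the DR0 weight would therefore gain almost nothing. The gain lies in using the mass of the test day.

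**The case against.** The strongest reply is that the plan is silent on scaling and re-weighing and does not exclude either. Watts is the unit in which power is calculated, and elsewhere the analysed variable is simply called metabolic cost. Moreover, same-day mass is largely recoverable: ground reaction forces are recorded in every trial, and mean vertical force over whole strides at steady speed equals total weight, prosthesis included. This stands, and it makes the remedy cheaper. It does not remove the point, because an analyst who follows the stated unit would leave mass change in the cross-day contrasts.

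It is also fair to say that random mass change is noise and does not favour any brand, and that the plan states no rule for choosing between brands. Both stand. A systematic shift needs mass to trend over sessions with order unbalanced. Brand order is not stated. The height order is fixed, since the recommended height always comes first, but nothing in the documents shows that mass trends.

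A reader might infer that absolute watts let the heaviest or fastest-paced runners dominate the group result. The documents do not support this. The ANOVA is within-subject, each runner's fitness-test speed is the same in every condition, and a common 3 m/s is also run. Steps 5 and 6 show only mild unequal weighting. A reader might also infer that watts would muddle the prescription algorithm in Section IV.G. That algorithm predicts stiffness and height, not watts.

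**Conclusion.** The point holds as a minor, inexpensive improvement. With power in watts and weighing stated only on Day DR0, mass change between sessions adds avoidable error to the brand contrasts and to each subject's choice of optimal height. The same-day choice of optimal stiffness is unaffected, and pooled means in watts give only somewhat more weight to heavier runners.

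The size is unknown. It rests on proportionality of power to mass, on 2% other error, and on an assumed between-day mass SD. At 0.5% the loss is slight (6% more variance). At 1% it is noticeable (25% more variance; power 0.72 to 0.63 under the further assumptions of step 4). The doubling at 2% requires mass variation as large as all other error combined and should be read as the upper end of the range shown.

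**What to change.** Record body mass at the start of every session by having the subject stand on the force-measuring treadmill, or derive it from mean vertical force over whole strides. Subtract the mass of the prosthesis worn, so that differences in prosthesis mass between brands are not divided out of the outcome. Analyse metabolic power as W/kg of that day's body mass, separately for the fitness-test speed and for 3 m/s, since W/kg does not remove differences in speed between runners. Name this unit in Section IV.C before data are seen.

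The cost is a few seconds per session, a known mass for each prosthesis, and one line of analysis wording. Scaling peak force and leg stiffness in the same way is optional.
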